9.2 Other Reportable Information

Certain information although not consistent with an SAE must be recorded, reported, and followed up in the same way as an SAE. This includes:

Vicore Pharma AB Version: 2.0 Trial ID: VP-C21-013 Date: 03-MAR-2023

- Any pregnancy that occurs during trial participation must be reported and administration of IMP must be terminated immediately. A pregnancy must be reported immediately to sponsor or designee. The pregnancy must be followed up to determine outcome including premature termination and status of mother and infant. The outcome must be reported even if there are no abnormal findings. Pregnancy complications and elective terminations for medical reasons must be reported as AEs or SAEs, as applicable. Spontaneous abortion must be reported as an SAE. In addition, the investigator must attempt to collect pregnancy information on any female partners of male trial participants who become pregnant while the male participant is enrolled in the trial. Pregnancy information must be reported to sponsor as described above.
- Lactation exposure to and IMP with or without an AE.
- Overdose of an IMP with or without an AE.
- Inadvertent or accidental exposure to an IMP with or without an AE.

9.3 Adverse Event Assessment Definitions

9.3.1 Severity

The investigator should assess the severity of all AEs according to the following definitions:

- Mild: awareness of symptoms, signs, illness, or event that is easily tolerated.
- Moderate: discomfort sufficient to cause interference with usual activity.
- Severe: incapacitating with inability to work or undertake further normal activities.

Note the distinction between seriousness and severity: The term severe is used to describe the intensity of the event and a severe event is not necessarily serious. The seriousness criteria serve as a guide for defining regulatory reporting obligations.

9.3.2 Relationship to IMP

Assessment of causality is based on the following considerations: associative connections (time and/or place), pharmacological explanations, previous knowledge of the drug, presence of characteristic clinical or pathological phenomena, exclusion of other causes, and/or absence of alternative explanations.

The investigator will assess the relationship to trial treatment for all AEs and SAEs. The relationship will be characterized using the following causality ratings:

- Related
- · Not related
- Not applicable

Causality assessment instructions are as follows:

Related: There is a reasonable possibility that the AE was caused by the drug. There is a reasonable time relationship to drug intake. The AE cannot be explained by disease or other drugs. There may or may not be information about de-challenge or re-challenge. Disappearance

Clinical Trial Protocol

Vicore Pharma AB Version: 2.0 Trial ID: VP-C21-013 Date: 03-MAR-2023

of the AE upon de-challenge supports this category. Reappearance upon re-challenge is strongly supportive.

Not related: There is no reasonable possibility that the event was caused by the IMP. The temporal relationship to drug administration makes a causal relationship improbable or other drugs or underlying disease or conditions provide plausible explanations.

Not applicable: This assessment can be used e.g. in cases where the patient did not receive any treatment with IMP.

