5.6 Withdrawal Criteria

Subjects are free to discontinue their participation in the trial at any time and for whatever reason without affecting their right to an appropriate follow-up investigation or their future care. If possible, the reason for withdrawal of consent should be documented.

Subjects may be discontinued from the trial at any time at the discretion of the investigator.

A subject who prematurely discontinues participation in the trial will always be asked about the reason(s) for discontinuation and the presence of any AEs. If a subject withdraws consent, the

Vicore Pharma AB Version: 2.0 Trial ID: VP-C21-013 Date: 03-MAR-2023

investigator must ask the subject if he/she is willing, as soon as possible, to be assessed according to the procedures scheduled for the end-of-trial visit (Visit 4). Any ongoing AEs will be followed-up as described in Section 9.6.

The primary reason for discontinuation/early withdrawal must be specified in the eCRF and final drug accountability must be performed. If the reason for discontinuation was an AE, the AE must be specified in the eCRF.

Subjects who are prematurely withdrawn from the trial for any reason except the occurrence of AEs assessed as related to the trial treatment, may be replaced.

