9 ADVERSE EVENTS

9.1 Adverse Event Definitions

An adverse event (AE) is defined as any untoward medical occurrence in a subject administered the IMP and which may or may not have a causal relationship with this IMP. An AE can therefore be any unfavorable and unintended sign (e.g. a significant abnormal laboratory finding, symptom, or disease temporally associated with the use of the IMP, whether or not considered related to the IMP

An adverse drug reaction (ADR) is any untoward and unintended response to an IMP assessed as related to any dose administered. Response means that the AE is assigned a causality assessment of "Related" to IMP.

An AE is considered "unexpected" if the nature, severity, or outcome is not consistant with the reference safety information in the current edition of the IB.

A Treatment Emergent Adverse Event (TEAE) is any sign, event or symptom that emerges during treatment having been absent pre-treatment, or worsens relative to the pre-treatment state.

A Serious Adverse Event (SAE) is any untoward medical occurrence that at any dose:

- Results in death.
- Is life-threatening (this refers to an event in which the subject was at risk of death at the time of the event; it does not refer to an event that hypothetically might have caused death if it was more severe.)
- Requires in-patient hospitalisation or prolongation of existing hospitalisation*.
- Results in persistent or significant disability or incapacity.
- Is a congenital anomaly or birth defect.

Medical and scientific judgement should be exercised in deciding whether expedited reporting is appropriate in other situations, such as important medical events that may not be immediately life-threatening or result in death or hospitalisation but may jeopardise the subject or may require intervention to prevent one of the other outcomes listed in the definition above. These should also usually be considered serious. Examples of such events are intensive treatment in an emergency room or at home for allergic bronchospasm; blood dyscrasias or convulsions that do not result in hospitalisation; or development of drug dependency or drug abuse.

*Exemptions may be made when hospitalization is due to:

- Routine treatment or monitoring of the investigated indication, not associated with any deterioration in the condition.
- Treatment that was elective or pre-planned, for a pre-existing condition that is unrelated to the indication under investigation and did not worsen.

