9.6 Follow-up on Adverse Events

All AEs should be followed until they have reached a final outcome (Recovered/resolved; Recovering/resolving; Not recovered/not resolved/ongoing; Recovered/resolved with sequelae; Fatal, Unknown) or the subject's participation in the trial ends, whichever comes first.

SAEs and severe, non-serious AEs considered related to IMP still ongoing after the trial end should be followed on a regular basis according to the investigator's clinical judgment until a final outcome has been established. The outcome category "Not recovered/not resolved/ongoing" may used as a final outcome in situations where the severity grade is no longer subject to change.

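### The Related and Not related causality definitions in section 9.3.2 are not complementary, so an adverse event with both a reasonable possibility of drug cause and another plausible explanation has no consistent rating

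*Combined protocol and SAP*

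**What the plan says.** Section 9.3.2 of the protocol gives three ratings: Related, Not related and Not applicable. The only example for the third is a patient who received no IMP, so it is not a middle category.

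Related opens with "There is a reasonable possibility that the AE was caused by the drug". It continues with "There is a reasonable time relationship to drug intake" and "The AE cannot be explained by disease or other drugs". The next sentence is expressly optional: "There may or may not be information about de-challenge or re-challenge".

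Not related opens with the opposite lead, that no reasonable possibility exists. Its second sentence gives two alternatives: timing that makes a causal link improbable, or that "other drugs or underlying disease or conditions provide plausible explanations".

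The rating is used elsewhere in the protocol:

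- Section 9.1: "An adverse drug reaction (ADR) is any untoward and unintended response to an IMP assessed as related to any dose administered".
- Section 5.6: subjects withdrawn early "for any reason except the occurrence of AEs assessed as related to the trial treatment, may be replaced".
- Section 9.6: "SAEs and severe, non-serious AEs considered related to IMP still ongoing after the trial end should be followed".
- Section 13.6.1: the overview of treatment-emergent events includes relationship to IMP.

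**The concern.** The two lead sentences divide all events cleanly. The sentences added to them do not. Related seems to require that no other explanation exists, while Not related accepts an event once another explanation is plausible. An event can have two credible causes, and the scale has no agreed place for it.

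Such events are foreseeable here. Type 2 diabetes is an inclusion criterion (section 5.3). Section 5.5.2 anticipates other medication and has it withheld around dosing, and section 5.5.1 requires fasting. Section 9.4 requires events from concurrent illness, concurrent medication and disease progression to be reported, so they will enter the database.

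At stake is whether such an event counts as an adverse drug reaction, whether it is followed after trial end if severe and non-serious, whether a subject withdrawn because of it may be replaced, and how it appears in the safety overview. The rating presumably also feeds the identification of SUSARs under section 9.5, although that section does not say whose assessment decides.

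**Working it through.** The protocol states no figure on this point, so the check is of the wording. Three yes/no facts are taken from section 9.3.2:

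- R: there is a reasonable possibility of drug cause.
- T: the timing is reasonable.
- E: disease or other drugs plausibly explain the event.

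One assumption is needed: the explanation sentence in Related and the explanation clause in Not related refer to the same fact E.

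Three readings of the text are possible:

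- A, every sentence is required: Related = R and T and not E; Not related = not R and (not T or E).
- B, any one Not related condition suffices: Related = R and T and not E; Not related = not R or not T or E.
- C, the lead sentence alone decides: Related = R; Not related = not R.

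| R | T | E | Reading A | Reading B | Reading C |
|---|---|---|---|---|---|
| yes | yes | yes | neither | Not related | Related |
| yes | yes | no | Related | Related | Related |
| yes | no | yes | neither | Not related | Related |
| yes | no | no | neither | Not related | Related |
| no | yes | yes | Not related | Not related | Not related |
| no | yes | no | neither | Not related | Not related |
| no | no | yes | Not related | Not related | Not related |
| no | no | no | Not related | Not related | Not related |

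Totals over the 8 combinations:

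- A: 1 Related, 3 Not related, 4 unassigned.
- B: 1 Related, 7 Not related.
- C: 4 Related, 4 Not related.

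The first row is the case at issue, and it receives three different answers. Under B the event is Not related although it contradicts that category's own lead sentence. Under C it is Related although it contradicts the explanation sentence.

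The rows with E but without R are Not related under all three readings. Another explanation alone therefore causes no difficulty; it must coincide with a reasonable possibility of drug cause.

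The timing sentences cause a smaller problem of the same kind, so removing only the two alternative-explanation clauses would not be enough. Under Reading A that would leave Related = R and T (2 of 8) and Not related = not R and not T (2 of 8), with 8 − 2 − 2 = 4 still unassigned. It would also strand the well-timed event with an obvious other cause and no reasonable possibility of drug cause, which is plainly Not related today.

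**The case against.** The best defence is that only the lead sentences are meant to bind. Section 9.3.2 begins with a list of considerations joined by and/or, which includes absence of alternative explanations, and section 9.4 restricts assessment to medically qualified personnel. On that view the later sentences are guidance, and Reading C gives a clean split. This is a fair reading, but the text does not state it. Only the de-challenge and re-challenge wording is marked as optional or supportive; the explanation sentence is flat.

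The consequences are also partly buffered. All SAEs go to the sponsor within 24 hours with a narrative, whatever their rating (section 9.5). Incidence of treatment-emergent events and SAEs is tabulated by treatment with no relatedness filter, and every treatment-emergent event is listed (section 13.6.1). Ratings are made blind (section 7.7), so the same ambiguity applies in both periods. Replacement is permitted, not required. These points limit the harm but do not settle how the event is to be rated.

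A reader might go further and infer that the wording biases the safety results towards Not related. The documents do not support that. They state no default, and how investigators would resolve the conflict is a guess about behaviour. What the text does show is that, read literally, the added clauses allow an event with a reasonable possibility of drug cause to be rated Not related.

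A reader might also take co-medication to be part of the design. It is anticipated but not required, and exclusion criterion 11 rules out insulin, GLP-1 agonists and several other drug classes.

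**Conclusion.** The point holds as an internal contradiction in section 9.3.2 that no other section resolves. It is a minor one. It concerns events in treated subjects that have both a reasonable possibility of drug cause and a plausible explanation by disease or other drugs. It does not reach every event with a diabetic or co-medication explanation.

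Its size cannot be computed, because the documents give no expected number of such events. One subject reclassified among 12 would move an incidence by 1/12 = 8.3 percentage points (1/14 = 7.1 to 1/10 = 10.0 over the 10 to 14 subjects in section 6.2). That is only the weight of one subject in a small trial; it does not estimate misclassification.

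The conclusion rests on the assumption that both explanation clauses describe the same fact, and on the absence of any rule of precedence in the text. The links to adverse drug reaction status, follow-up, replacement and the safety overview are stated in the protocol. The link to SUSAR identification is an inference.

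**What to change.** Add a sentence to section 9.3.2 stating that the lead sentence alone, a reasonable possibility or none, decides between Related and Not related. Reword both the alternative-explanation and the timing sentences in the two definitions as considerations that support the judgement, not as conditions for it. This gives the Reading C split, with each event in a treated subject in exactly one category. Carry the same wording into the eCRF guidance.

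The cost is a few wording edits. The downside is that a few more events may be classed as related.

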9.3.3 Outcome

The investigator will be asked to record the most appropriate outcome of the following categories:

- Recovered/resolved
- Recovering/resolving
- Not recovered/not resolved/ongoing
- Recovered/resolved with sequelae
- Fatal
- Unknown

9.4 Recording of Adverse Events

All events meeting the definition of an AE must be reported in the period from the subject has signed the informed consent form until the end-of-trial participation (Visit 4).

At each visit the subject will be asked about AEs in an objective manner, e.g.: "Have you experienced any problems since the last visit?". They will also be asked if they have been hospitalized, had any accidents, usen any new medications, or changed concomitant medication regiments (both prescription and over the counter medication).

Only medically qualified personnel are allowed to assess AEs.

AEs must be reported on the AE page of the eCRF. The diagnosis should be recorded, if available. If no diagnosis is available each sign and symptom should be recorded as individual AEs.

Information to be collected includes type of event, time of onset, investigator's assessment of severity and relationship to trial treatment, time of resolution of the event, seriousness, as well as any required treatment or evaluations, and outcome. The AEs resulting from concurrent illnesses, reactions to concurrent illnesses, reactions to concurrent medications, or progression of disease states must also be reported. For follow-up of AEs please refer to Section 9.6.

The Medical Dictionary for Regulatory Activities (MedDRA) will be used to code all AEs.

Any medical condition that is present at the time that the subject is screened for the trial and which does not deteriorate should not be reported as an AE. However, if the condition deteriorates/ worsens at any time during the subject's participation in the trial, it should be recorded as an AE.

Vicore Pharma AB Version: 2.0 Trial ID: VP-C21-013 Date: 03-MAR-2023

Abnormal laboratory values shall be recorded as AEs if assessed as clinically significant by the investigator. In that case, the severity will be assessed as per above. Laboratory abnormalities that are associated with an already reported medical condition will not be reported as separate AEs but will be used for the assessment of the associated medical condition (e.g., increased neutrophil count in case of a reported infection or increased glucose in a patient with diabetes).

Changes in the severity of an AE should be recorded to allow an assessment of the duration of the event at each level of intensity to be performed. An AE characterized as intermittent requires documentation of the onset and duration of each episode.

9.5 Reporting of Serious Adverse Events

Any AE which meets the definition of a SAEs must be reported within 24 hours of obtaining knowledge of the event. The information to be reported will include assessment of severity, causal relationship to IMP or trial procedures, action taken, outcome, and a narrative description of the course of the event.

The sponsor is responsible for notifying the relevant Health Authorities in compliance with applicable legislation. All suspected unexpected serious adverse reactions (SUSARs) are subject to expedited reporting to Health Authorities.

The investigator is responsible for notifying Ethics Committees (ECs) directly as per EC requirements.

The trial specific SAE form must be used when reporting to the sponsor.

Additional information may be subsequently provided.

The SAE form and all other relevant documents supporting the reported SAE (e.g. diagnostic procedures, hospital records, autopsy reports) must be faxed or scanned/emailed to the sponsor or sponsor's designee using the following e-mail address [contact].

9.6 Follow-up on Adverse Events

All AEs should be followed until they have reached a final outcome (Recovered/resolved; Recovering/resolving; Not recovered/not resolved/ongoing; Recovered/resolved with sequelae; Fatal, Unknown) or the subject's participation in the trial ends, whichever comes first.

SAEs and severe, non-serious AEs considered related to IMP still ongoing after the trial end should be followed on a regular basis according to the investigator's clinical judgment until a final outcome has been established. The outcome category "Not recovered/not resolved/ongoing" may used as a final outcome in situations where the severity grade is no longer subject to change.

10 CHANGES TO TRIAL CONDUCT

10.1 Protocol Amendments

Before implementation of substantial changes (as defined in EU Clinical Trials Directive (2001/EC/20)) unless considered an Urgent Safety Measure, approval/favourable opinion must be obtained from the appropriate regulatory authority(ies) and IEC(s).

Clinical Trial Protocol

Vicore Pharma AB Version: 2.0 Trial ID: VP-C21-013 Date: 03-MAR-2023

10.2 Premature Termination of the Trial

In case of premature termination of the trial, health authorities and IECs will be notified in writing, including the reason for premature termination.

Conditions that may warrant premature termination of the trial include, but are not limited to the following:

- The discovery of an unexpected and significant or unacceptable risk to the subjects enrolled in the trial.
- A decision of the sponsor to discontinue development of the drug.

10.3 Premature Termination of a Trial Site

The sponsor can decide to prematurely terminate a site. Conditions that may warrant termination include, but are not limited to:

- Insufficient adherence to protocol requirements.
- Failure to enrol subjects at an acceptable rate.

Clinical Trial Protocol

Vicore Pharma AB Version: 2.0 Trial ID: VP-C21-013 Date: 03-MAR-2023

11 DATA HANDLING AND RECORD KEEPING

11.1 Data Management

The data management routines include procedures for handling of the eCRF, database set-up and management, data entry and verification, data validation, QC of the database, and documentation of the performed activities including information of discrepancies in the process. The database, data entry screens, and program will be designed in accordance with the CTP.

Data validation/data cleaning procedures are designed to assure validity and accuracy of clinical data. These procedures consist of computerised online edit checks identifying e.g., data values that are outside the allowed range and SAS-programmed batch checks on data exports. All trial-specific and standard data validation programming will be tested prior to being used on final data.

Detailed information on data management will be described in a trial-specific Data Management Plan (DMP).

11.2 Data from Clinical Trial Site

Data from clinical trial site will be entered in an eCRF. The eCRF will be a 21 CFR part 11 compliant, password protected and validated system.

The investigator will sign relevant eCRF sections by use of an electronic signature. Only the investigator (i.e., medically qualified personnel) can sign data on medical assessments. Any corrections made by the investigator or authorised staff to the eCRF after original entry will be documented in an audit trail. The person making the change and the date, time and reason for the change will be identified in the audit trail. Changes to the data already approved/signed by an investigator will require re-signature by the investigator. The investigator (principal investigator or sub-investigator) will sign all patient data in the eCRF by an electronic signature.

Subject data will be recorded pseudonymized and the subjects will be identified only by a screening number and a randomisation number.

The monitor will check the eCRF for accuracy and completion and perform source data verification. Data entered in the eCRF will be verified against source data.

